## Figure 2: Study Design Scheme and Timelines

**Study Device:** The Medtronic 670G insulin pump with Medtronic Guardian® 3 Sensor and Contour® Next Link blood glucose meter (Medtronic, Northridge, CA) has 2 modes: open (manual) and closed (auto). The research team will set the necessary parameters for open mode (basal rates, glucose targets, active insulin time, carbohydrate-to-insulin ratios, and correction [sensitivity] factors) at baseline and throughout the study period. For closed mode, the team will set the active insulin time and carbohydrate-to-insulin ratios. The HCL system requires multiple days of data from open mode to personalize HCL control parameters in closed mode, therefore subjects will be started in open mode and transitioned to closed mode after 5 days. The HCL system algorithm utilizes sensor glucose to deliver microboluses every 5 minutes to achieve the target glucose level. The glucose target is fixed at 120 mg/dL but one can temporarily set the glucose target to 150 mg/dL for exercise. The closed mode requires calibrations (optimally 3-4 times daily) and announcements for carbohydrate consumption and exercise. Participants will be

counseled that finger stick blood glucose values must be checked and used for pre-meal and correction insulin boluses. Participants will be counseled that should they experience symptoms of hypoglycemia or hyperglycemia, then should confirm with a finger stick blood glucose measurement and treat according to the value obtained. Patients can stop closed mode therapy at any time and will be given specific instructions on when this is appropriate. The system exits open mode for a variety of reasons (e.g., lost sensor signal, persistent glucose readings below or above predesignated limits, pump occlusions, insulin delivery rates persistently below or above predesignated limits), which can be recorded. These parameters have been well-described in previous studies. For this study, glucose targets will be set at 80-100 mg/dL during the day and 90-110 mg/dL over night for both arms of the study during pregnancy. Bolus targets will be set at 90-120 mg/dL during the day and 100-130 mg/dL over night in the post-partum period.

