#### **D. Description, Risks and Justification of Procedures and Data Collection Tools:**

##### Risks:

Wearing insulin infusion sets and sensors can cause adverse skin reactions such as pain at the site of infusion set or sensor insertion. The adhesive pads may cause skin erythema for 1 to 2 days or more. An allergic reaction to 1 or more parts of CSII and CGM devices may occur which can be mild, moderate, or severe (rare). In rare cases, an infection at the infusion set or sensor site may occur. In rare cases, the sensor or needle may break inside the body and would require a minor surgical procedure to remove it.

These risks are likely during the run-in phase, but individuals unable to wear devices will not continue on. We also screen out individuals with a history of serious skin reactions to adhesives. These issues remain possible as the study continues, but will be less likely in those women able to be randomized.

Severe hypoglycemia is defined as a hypoglycemic episode requiring assistance of a 3rd party or hospitalization with or without an SMBG. The risk of severe hypoglycemia is high in pregnancy, especially in the 1st trimester. It will be reported as a severe adverse event (SAE). A hypoglycemic event “requiring assistance” is determined when the subject is unable to treat the event on her own. We have determined our sample size based on the ability to compare rates of severe hypoglycemia between groups. Severe hypoglycemia can lead to coma, seizure, or death, however the likelihood of these extreme adverse events is low. Any untoward event resulting in hospitalization, extension of hospitalization, death, or threat of death will also be considered an SAE. SAEs will be reported to the Drug Safety Monitoring Board (DSMB).

Medtronic CGM systems may experience reduced sensor accuracy (falsely elevated glucose levels) if the user takes acetaminophen-containing products. The level of sensor glucose inaccuracy may vary by participant and may depend on the quantity of acetaminophen administered. Therefore, all participants will be advised to mark acetaminophen use on paper and in the insulin pump as an “Injection” event marker. They will also be advised to rely on fingerstick glucose measurements for 12 hours after acetaminophen use for insulin dosing.

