To address **Specific Aim 1**, we will compare percent of time spent in the SH range of <54 mg/dL on CGM (primary outcome) using a non-inferiority t-test with a margin of 1%. Counts of DKA and adverse skin reactions (secondary outcomes) will be compared between groups (HCL vs. SAPT) using t-tests for normally distributed variables and Wilcoxon Rank-Sum test for non-normal variables. As the purpose of this study is to demonstrate that HCL has a similar safety profile compared to SAPT during pregnancy, we will use a non-inferiority test. As a secondary analysis of events such as SH, DKA, and skin reactions, we will account for potential differential follow-up times due to miscarriage, drop-out, and withdrawal using Poisson regression with an offset for follow-up time. To address **Specific Aim 2**, we will compare CGM glucose variables (primary outcomes for glucose variables will be time spent <54, <63, 63-140, >140, >180 mg/dL; secondary outcomes will be glucose SD, J index, HBGI, LBG, MAGE, and CONGAn) and fear of hypoglycemia score between groups (HCL vs. SAPT) using t-tests for normally distributed variables and Wilcoxon Rank-Sum test for non-normally distributed variables. We will examine the buckets of time spent in each range (hypoglycemia, in range, and hyperglycemia) by day and night, as well as day-to-day variation. Mean glucose variables and hypoglycemia fear scores will be compared during each trimester of pregnancy and 4-6 weeks post-partum using mixed models. To address **Specific Aim 3**, we will compare SF-36 scores, insulin device satisfaction and glucose device satisfaction by group (HCL vs. SAPT) using t-tests if scores are normally distributed and Wilcoxon Rank-Sum test if scores are non-normal. We will analyze changes in INSPIRE Questionnaire scores over time in the HCL group. **Specific Aim 4** is an exploratory aim, and for this aim we will examine rates of fetal loss, preeclampsia, cesarean section, LGA, and neonatal hypoglycemia using Chi-square tests. We will account for potential differential follow-up times due to miscarriage, drop-out, and withdrawal using Poisson regression with an offset for follow-up time as a sensitivity analysis, in addition to the proposed chi-square tests in the exploratory analyses of fetal loss, preeclampsia, Caesarean section, LGA, and neonatal hypoglycemia. We will use mixed models to analyze changes in repeated measures, such as glycemia variables and hypoglycemia fear scores by trimester. We will evaluate the percent of time spent in closed loop by trimester as a feasibility outcome that is important to the next step of a larger clinical trial with efficacy outcomes.

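### After acetaminophen, automated insulin in auto mode cannot follow the 12-hour fingerstick advice, and the marked hours enter the CGM primary outcomes with no sensitivity analysis

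*Combined protocol and SAP*

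**What the plan says.** Section IV.D (Risks) gives the warning: "Medtronic CGM systems may experience reduced sensor accuracy (falsely elevated glucose levels) if the user takes acetaminophen-containing products". It adds: "The level of sensor glucose inaccuracy may vary by participant and may depend on the quantity of acetaminophen administered". Two instructions follow for both arms. Use is to be recorded: "all participants will be advised to mark acetaminophen use on paper and in the insulin pump as an “Injection” event marker". On dosing: "They will also be advised to rely on fingerstick glucose measurements for 12 hours after acetaminophen use for insulin dosing".

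Section IV.C (Study Device) describes what auto mode does: "The HCL system algorithm utilizes sensor glucose to deliver microboluses every 5 minutes to achieve the target glucose level". On the target it says: "The glucose target is fixed at 120 mg/dL but one can temporarily set the glucose target to 150 mg/dL for exercise". In the same section participants are "counseled that finger stick blood glucose values must be checked and used for pre-meal and correction insulin boluses".

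In SAPT the sensor moves no insulin by itself, because section IV.C disables both low-glucose suspend features in that mode.

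For Specific Aim 1, section IV.F states: "we will compare percent of time spent in the SH range of <54 mg/dL on CGM (primary outcome". The Aim 2 glucose primaries (time below 54, below 63, 63-140, above 140 and above 180 mg/dL) are CGM measures too. Neither the data-collection text (IV.C, Safety Factors and Glycemic Factors) nor section IV.F mentions the acetaminophen markers. The Data Monitoring text in IV.D has only general checks of outliers and missing values.

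**The concern.** There are two linked gaps.

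**Protocol.** The 12-hour advice covers insulin dosing without qualification. In auto mode part of the dosing is automatic and rests on the sensor reading that the advice says not to rely on. If the reading is falsely high, the system may give more insulin than true glucose warrants. That is a hypoglycemia hazard in the arm whose hypoglycemia safety Aim 1 is meant to test.

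**Analysis.** The trial collects a marker for hours in which the sensor may be wrong and then never uses it. A falsely high sensor hides some true lows in both arms. In HCL it can also cause lows, and these would be hidden as well. The error therefore need not cancel in the HCL-minus-SAPT difference, and the Aim 1 test is a non-inferiority test with 10 women per group. If handling of the marked hours is decided only after the data have been seen, that choice can itself affect the conclusion.

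**Working it through.** **1. Which doses can follow the advice.**

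| Dose | Driven by | Can follow the 12-hour advice? |
|---|---|---|
| SAPT, all doses | Programmed basal and user boluses; suspend features off | Yes |
| HCL, meal and correction boluses | Fingerstick (Study Device) | Yes |
| HCL, automated microboluses | Sensor, every 5 minutes | Not while in auto mode |

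Elsewhere the protocol does say what happens to auto mode: for high-dose steroids, for labor and delivery, for conditions that cut insulin needs, and for device malfunction. Acetaminophen is on none of these lists.

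**2. The plan's own figure.** Power and Sample Size Calculations gives 10 per group, SD 1.1%, margin 1.5%, one-sided alpha 0.025 and 80% power. The standard error is 1.1 x sqrt(2/10) = 0.492 and the noncentrality is 1.5/0.492 = 3.05. With the noncentral t on 18 df, power is 82.2%; with 9 per group it is 77.5%. So 10 is the smallest group size with at least 80% power, and the figure reproduces.

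**3. Share of CGM hours affected (frequency assumed; the documents give none).**
- One window per month: 12/(30.4 x 24) = 1.6%
- One per week: 12/168 = 7.1%
- 3.5 per week: 42/168 = 25%

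**4. Bias inside the affected hours (a sketch on assumed inputs).** Let the sensor read true glucose plus b. SAPT true glucose is unchanged. HCL true glucose falls by r x b, where r is the share of the false rise that the loop removes. Glucose is taken as normal, with F(54; mean, SD) the proportion below 54 mg/dL.

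Bias = (recorded HCL - recorded SAPT) - (true HCL - true SAPT). A negative value favours HCL for time below 54.

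Equal arms (mean 128, SD 45), b = 30 mg/dL:

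| r | HCL true / recorded <54 (%) | SAPT true / recorded <54 (%) | Bias in window (points) | Overall, 1 per month | Overall, 1 per week | Overall, 3.5 per week |
|---|---|---|---|---|---|---|
| 0 | 5.00 / 1.04 | 5.00 / 1.04 | 0.00 | 0.00 | 0.00 | 0.00 |
| 0.5 | 9.49 / 2.40 | 5.00 / 1.04 | -3.13 | -0.05 | -0.22 | -0.78 |
| 1 | 16.41 / 5.00 | 5.00 / 1.04 | -7.44 | -0.12 | -0.53 | -1.86 |

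At one window per week, b = 10 gives 0.00, -0.03 and -0.06; b = 60 gives 0.00, -0.75 and -1.99.

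Unequal arms: HCL mean 128 and SAPT mean 137, as in the pregnancy crossover study in the Background; SDs of 35 and 48 assumed; b = 30:

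| r | Bias in window, time <54 (points) | Overall, 1 per week | Bias in window, time 63-140 (points) |
|---|---|---|---|
| 0 | +1.68 | +0.12 | -11.1 |
| 0.5 | -0.78 | -0.06 | -5.7 |
| 1 | -5.45 | -0.39 | +6.8 |

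For time in range a positive value favours HCL, so here the bias runs against HCL in two of the three cases.

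**5. Effect on the Aim 1 test.** At a true difference equal to the margin, a bias d towards HCL gives noncentrality d/0.492. The one-sided error rate of 2.5% becomes 4.2% at d = 0.12, 6.2% at 0.22 and 17.4% at 0.53. This does not depend on whether the margin is 1% (Statistical Analysis Plan) or 1.5% (power section).

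**Caution on size.** The sketch assumes that 5.0% of true time is below 54 mg/dL in the equal-arms case. The Background study reports only 1.9% (HCL) and 1.8% (SAPT) below 63 mg/dL. The sketch may therefore overstate the bias.

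**The case against.** The case on the other side has force on several points.

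- **The advice can be followed in part, and auto mode can be left.** Meal and correction boluses already rest on fingersticks. The Study Device text lets women stop closed mode at any time and promises specific instructions on when to do so. Those instructions and the appendix handouts are not in the supplied text and may cover acetaminophen. This stands. A reader might infer that HCL participants cannot comply at all; the documents support that only for automated microboluses while auto mode is on.
- **The warning is conditional.** It says that accuracy may be reduced, by an amount that may vary with the woman and the quantity taken. This stands. The 12 hours are a dosing precaution, and the documents do not say that every reading in them is wrong.
- **The direction of bias is not established.** This stands. Full loop response is an assumption: the system is calibrated several times a day and has automatic mode exits for persistently high readings and for insulin delivery beyond its limits.
- **Safety does not rest on CGM alone.** Severe hypoglycemia episodes are also a primary outcome, are asked about at every visit and drive the stopping rules. This limits what is at stake.
- **Excluding the hours has its own bias.** Marking is self-reported, after randomisation and open-label, the plan promises intention to treat, and exclusion drops the hours of concern from a safety endpoint. This stands against exclusion as the primary analysis, but not against a sensitivity analysis.

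None of this supplies the missing link between acetaminophen and auto mode, or a planned use for the markers.

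**Conclusion.** Two points hold on the text alone. As written, the 12-hour advice cannot govern automated insulin while a woman stays in auto mode, and no supplied section says what happens to that mode. The marked hours also enter the CGM primary outcomes with no flag or sensitivity analysis.

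The effect on the results is conditional. The error may hide time below 54 mg/dL more in HCL. With equal arms and a 30 mg/dL error, the bias is 0.00 to -0.12 points at one window per month and 0.00 to -0.53 at one per week. It reaches -1.86 only with use on half of all days and full loop response. Frequency of use, error size, loop response and glucose spread are all assumed.

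A reader might infer that the error favours HCL on every CGM primary outcome. The documents do not support that. For time below 54 the bias vanishes with equal arms and no loop response, and it can turn against HCL when SAPT glucose is more variable. For time in range no direction can be claimed.

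The plan should be amended on both points. The gap does not by itself invalidate the design.

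**What to change.** 1. **Protocol.** Reconcile the acetaminophen text in section IV.D (Risks) with the auto-mode description in section IV.C (Study Device), so that a woman in auto mode can carry out the 12-hour instruction. If the participant instructions already cover this, cite them there. The clinical rule is for the investigators to choose.
2. **SAP, section IV.F.** Keep the all-data analysis as primary. Prespecify a sensitivity analysis of the Aim 1 and Aim 2 CGM primary outcomes in which sensor values in the 12 hours after each marked acetaminophen use are set to missing in both arms.
3. **Reporting.** Give, by arm, the number of such windows and the meter readings below 54 and below 63 mg/dL within them. The meter readings matter because setting sensor hours to missing also removes any true lows in them.

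The cost is a short protocol clarification and a little extra programming on markers and meter downloads already collected. Unmarked use will not be captured. Settle the rule before any comparison of CGM outcomes by arm.

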#### *Data Monitoring*

Data will be collected and managed using REDCap (Research Electronic Data Capture). The database is hosted at the University of Colorado Denver Development and Informatics Service Center (DISC), which will be a central location for data processing and management. This server has a high level of security, controlled access, daily back-up, and long-term retention of back-up files. All members of the BDC research team in this study have individual computers that are part of the institution network with institutional oversight of security. Field and range checks will be programmed to minimize data entry errors. Data distribution will be checked periodically and outliers verified; missing data will be tracked and checked.

#### Justification of Procedures:

There may not be benefits to subjects. However, CSII and CGM therapies have both been shown to have benefits over MDI and SMBG, respectively, thus for women who were not on these technologies prior to study inclusion, they will likely experience better glucose control and potential better gestational outcomes.

Both CSII and CGM therapies have been investigated in pregnancies associated with diabetes, as has SAPT. Thus, the SAPT arm incurs no extra risks. Only investigational HCL systems have ever been studied in pregnancy before now. The knowledge gained from a study examining a device being used by the public but in a new capacity is extremely valuable. The subjects would receive the same, high-quality care throughout pregnancy regardless of study participation, but would additionally be under closer supervision because of the new therapy being used. This supervision would include

prompt reporting of AEs and SAEs to the study MDs, DSMB, and IRBs, as well as interim safety analyses. Thus, the risks to the subjects would be minimized as much as possible, while the knowledge gained would be high impact and extremely important.

Given the importance of tight glycemic control in pregnancy, there are risks of HCL therapy that has never been studied during pregnancy. However, subjects will get additional education and personalized nutrition guidelines for carbohydrate counting and adhering to ADA guidelines for nutrition with limitations on carbohydrate content for each meal and snack to limit post-prandial excursions. In addition, they will be in contact with research staff who are also experienced clinicians every week during the pregnancy to change pump settings, optimize care, and reduce extreme glycemic variations that could have adverse effects. Finally, in studies outside of pregnancy, HCL therapy has been shown to improve glucose control and reduce hypoglycemia over CSII alone and SAPT, thus we feel that under controlled conditions, HCL therapy has great potential to have similar effects in pregnancy, which would outweigh the potential risks.

#### **E. Potential Scientific Problems:**

Potential Pitfall #1: The HCL system does not allow a lower glucose target than 120 mg/dL. An estimated average glucose of 120 mg/dL correlates to an A1C of 5.8%, which is within the recommended target range in pregnancy. A study among women with T1D using CGM found that they spent ~8 hours/day with a glucose >140 mg/dL and ~3.25 hours/day with glucose <70 mg/dL in each trimester. Both extremes are detrimental. Maternal hypoglycemia is one of the major barriers to achieving optimal glucose control. Maternal SH can lead to coma, road traffic accidents, and death. Animal studies link hypoglycemia early in gestation with growth retardation and congenital anomalies. In multiple studies demonstrating good overall glucose control among women with diabetes, rates of infant LGA and macrosomia remained high. This phenomenon may result from maternal hypoglycemia leading to treatment with carbohydrate consumption, fetal hyperinsulinemia, and then excess fetal growth. Moreover, there is evidence that an intervention that improves TIR (even without a large difference in A1C) can improve maternal and fetal outcomes. Studies in non-pregnant groups using the 670G system demonstrate little hypoglycemia among adults (3.4% time  $\leq$ 70 and 0.6%  $\leq$ 50 mg/dL) with increased TIR and decreased hyperglycemia, thus this system will potentially also improve overall maternal glucose control and reduce adverse pregnancy outcomes. Benefits of HCL therapy will likely outweigh risks. The study protocol includes collection of safety measurements throughout and review of these data through an independent DSMB. Should evidence arise that HCL is associated with significant harm, directive measures will be taken immediately.

Potential Pitfall #2: The HCL system may not remain in auto mode continuously. The HCL system is designed to leave HCL mode under certain conditions that would affect its efficacy (e.g., prolonged loss of sensor signal). Thus, all subjects randomized to HCL therapy will also have regular adjustments made to their basal patterns and bolus wizard settings for the manual mode. Manual mode is equivalent to SAPT. Data will be collected weekly to assess frequency and etiology for leaving HCL mode. HCL exits due to subject behaviors will be addressed promptly (e.g., not wearing the sensor). A previous study done under free-living conditions wherein patients had significant alternations in glucose from exercise, medication changes, and the like showed that participants remained in HCL mode ~88% of the time. Subjects in this proposal who have HCL mode enabled  $\leq$ 80% of the time will be identified so that corrective measures can be taken (e.g., if HCL

is exited from under-calibrations then the subject will be reminded that she must calibrate 3-4 times each day).

#### F. Data Analysis Plan:

##### Statistical Analysis Plan:

Data will be blinded to the study statistician. For the **interim safety analysis**, after the first 5 participants in each group have completed the 1st trimester, we will analyze the interim data to compare episodes of SH between groups to ensure no increased risk of SH with HCL therapy. Episodes of SH will be used for the interim analysis as SH events can be life-threatening for pregnant women and their fetuses. If interim safety analyses demonstrate no increased harm in either group, then the statistician will remain blinded until the end of the study. If the interim safety analyses demonstrate increased harm in one group necessitating evaluation of whether the study should be stopped, then the statistician will be unblinded at that point.

To address **Specific Aim 1**, we will compare percent of time spent in the SH range of <54 mg/dL on CGM (primary outcome) using a non-inferiority t-test with a margin of 1%. Counts of DKA and adverse skin reactions (secondary outcomes) will be compared between groups (HCL vs. SAPT) using t-tests for normally distributed variables and Wilcoxon Rank-Sum test for non-normal variables. As the purpose of this study is to demonstrate that HCL has a similar safety profile compared to SAPT during pregnancy, we will use a non-inferiority test. As a secondary analysis of events such as SH, DKA, and skin reactions, we will account for potential differential follow-up times due to miscarriage, drop-out, and withdrawal using Poisson regression with an offset for follow-up time. To address **Specific Aim 2**, we will compare CGM glucose variables (primary outcomes for glucose variables will be time spent <54, <63, 63-140, >140, >180 mg/dL; secondary outcomes will be glucose SD, J index, HBGI, LBG, MAGE, and CONGAn) and fear of hypoglycemia score between groups (HCL vs. SAPT) using t-tests for normally distributed variables and Wilcoxon Rank-Sum test for non-normally distributed variables. We will examine the buckets of time spent in each range (hypoglycemia, in range, and hyperglycemia) by day and night, as well as day-to-day variation. Mean glucose variables and hypoglycemia fear scores will be compared during each trimester of pregnancy and 4-6 weeks post-partum using mixed models. To address **Specific Aim 3**, we will compare SF-36 scores, insulin device satisfaction and glucose device satisfaction by group (HCL vs. SAPT) using t-tests if scores are normally distributed and Wilcoxon Rank-Sum test if scores are non-normal. We will analyze changes in INSPIRE Questionnaire scores over time in the HCL group. **Specific Aim 4** is an exploratory aim, and for this aim we will examine rates of fetal loss, preeclampsia, cesarean section, LGA, and neonatal hypoglycemia using Chi-square tests. We will account for potential differential follow-up times due to miscarriage, drop-out, and withdrawal using Poisson regression with an offset for follow-up time as a sensitivity analysis, in addition to the proposed chi-square tests in the exploratory analyses of fetal loss, preeclampsia, Caesarean section, LGA, and neonatal hypoglycemia. We will use mixed models to analyze changes in repeated measures, such as glycemia variables and hypoglycemia fear scores by trimester. We will evaluate the percent of time spent in closed loop by trimester as a feasibility outcome that is important to the next step of a larger clinical trial with efficacy outcomes.

For women who discontinue CGM therapy during the study, we will do an intention to treat analysis of above-stated outcomes. The alpha level will be 0.05 for all analyses, except the non-inferiority tests (alpha = 0.025). The use of mixed models and Poisson regression will allow for analysis of data for the portion of the study completed with CGM therapy.

**Power and Sample Size Calculations:** The primary outcome for **Specific Aim 1** is percent of time spent <54 mg/dL on CGM. With a sample size of 10 women per group (20 study completers), we will have 80% power to detect non-inferiority using a one-sided alpha of 0.025 and a non-inferiority margin of 1.5% of time spent <54 mg/dL for HCL compared to SAPT, using estimates of variability from the PI's current study of CGM use during pregnancy. The standard deviation of time spent <54 mg/dL based on data from the PI's current study of CGM use during pregnancy was 1.1%. For **Specific Aim 2**, with a sample size of 10 women per group (20 study completers), we will have 83% power to detect a difference in time spent in target glucose range (65-140 mg/dL, this range was used in the power calculations because at that time there was no consensus on optimal time in range in pregnancy) of 3.3 hours/day (13.8%) between HCL to SAPT, assuming a standard deviation of 2.5 hours/day (effect size=1.0 SD). This is similar to effect sizes reported in another artificial pancreas study showing a difference of 2.5 hours/day (10.4%) between groups and a study of HCL in pregnancy (in a crossover design) showing a difference of 3.6 hours/day (15.2%). While this study is not powered to detect significant differences in maternal-fetal outcomes as described in **Specific Aim 4**, our goal is to provide estimates and preliminary data on these outcomes to inform the sample size needed for a larger trial focused on these outcomes, once the safety of the HCL system in pregnancy has been established.

